Some studies have already been conducted in order to investigate the effects of different cleaning protocols for acrylic removable orthodontic appliances and may also help to reduce the risk of oral diseases related to biofilm growth, some different processes have been described such as denture cleaners, enzymatic solutions, chlorhexidine, sodium hypochlorite, or homemade solutions containing vinegar or citric acid (**Eichenauer *et al.*, 2011**). The two major approaches used for denture cleaning are mechanical and chemical methods. Mechanical methods include brushing (using water, soap, toothpaste, or abrasives) and ultrasonic treatment. Mechanical cleaning with brushes is inexpensive and common, but elderly and disabled patients might face difficulties with this method because of poor motor coordination, poor dexterity, and low motivation. There is evidence that mechanical cleaning with toothpastes can result in significant wear of conventional acrylic resins. Chemical method includes immersion of dentures in different cleansing solutions. Immersion in cleansing solution is an inexpensive, easy, and comfortable alternative procedure. Moreover, the cleansing solution can reach undercuts of the denture base that are difficult to clean mechanically, resulting in more efficient cleaning (**Schwindling *et al.*, 2014**).

No study is conducted to evaluate the most effective method used to remove biofilm from removable orthodontic appliance.

Research question:

What is the most effective method of cleaning an acrylic based removable orthodontic appliance?

Research hypothesis

The null hypothesis: There is no difference between the different methods of cleaning acrylic based removable orthodontic appliances.

Aims of the study:

The aims of the current study are:

1. To evaluate the effects of different cleaning regimes i.e. chemical and mechanical on biofilm formation of an acrylic based removable orthodontic appliance.
2. To find out if surface modification i.e. polished acrylic fitting surface, have an impact on cleaning the biofilm formation.

Methodology

Study design:

An in vivo study.

Setting:

It is double-blind, parallel, randomized clinical trial conducted in the orthodontic clinic after obtaining the ethical approval from the ethics committee of the department.

Subjects:

Orthodontic patient will be selected to wear a removable appliance for the study period.

Sample size:

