Thirteen orthodontic patients for each group will be selected to wear a removable orthodontic appliance for the study period (**Lima et al., 2006**) and will be instructed for the cleaning protocol according to the manufacturer's instructions.

Inclusion criteria:

- Presence of full upper permanent dentition;
- Well-aligned teeth or mild crowding (less than 3mm);

- No history of sensitivity to any ingredient contained in the cleaning materials;
- Nonsmoker;
- Caries free.

Exclusion criteria:

- Participant taking steroid-based or antibacterial mouthwash or broad-spectrum antibiotics;
- Mouth breather;
- Participant taking medication that reduces salivary flow;
- Pregnant or lactating female (**Albanna *et al.*, 2017**).

All of the study steps were explained to the participants verbally and in writing, written informed consent will be obtained from each participant.

Materials and instruments**Materials used for orthodontic removable appliance fabrication:**

- Acrylic powder and monomer (Orthocryl, Dentaaurum, Ispringen, Germany).
- 0.7 mm stainless steel wire (Spring hard, Dentarum, Ispringrn, Germany).
- Adam's plier.
- Sticky wax.
- Separating medium.
- Cutter.
- Wax knife.
- Mold material.

Materials used for cleaning regimes:

- 1-Brush (dental or denture brush) with chlorhexidine (CHX) toothpaste.
- 2-Chemical cleaning i.e. Lacalut cleaning tablet.
- 3-Combination of brushing with CHX toothpaste and cleaning tablet.

Materials and equipment used form microbial isolation and identification:

1. Calcium alginate swab.
2. Calgon ringer solution.
3. Bijou tube.
4. Glass beads.
5. Phosphate buffered saline (PBS).
6. Anaerobic cabinet.
7. Vortex machine.
8. Culture media.

A. Mitis-Salivarius Agar (MSA): This agar is a commonly used selective medium for isolating and quantifying *S. mutans* in many cariology clinical and epidemiological studies (**Xiao *et al.*, 2016**).

B. Mannitol salt agar: Is a commonly used selective and differential growth medium in microbiology. It contains a high concentration (about 7.5%-10%) of salt (NaCl), making it selective for Gram-positive *Staphylococcus aureus* and *epidermidis* since this level of salt is inhibitory to most other bacteria (**Bachoon *et al.*, 2008**).

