The acrylic tiles (5mm in diameter and 1mm thickness) will be placed and fixed into the holes, created by the metal discs, using sticky wax. The acrylic samples will be randomly seated as shown in figure 3.

The appliance will be sterilized using proper sterilization protocol.

Figure 3: The acrylic base containing the acrylic samples.

Method for biofilm detection

The removable appliance will be assigned randomly and blindly and fitted into the oral cavity of the patient for one week. Each individual will be given a pack containing the cleansing pack and an instruction sheet with a web link describing the cleaning regimen for his/ her appliance. The packs are similar in shape and color and will be prepared by a third person who does not know the purpose of the study. The volunteer will be grouped into three groups:

Group 1: patients will be instructed to brush both sides of the removable appliance once a day for 1 minute before bedtime using the toothbrush and the CHX toothpaste provided and water (**Albanna *et al.*, 2017**).

Group 2: patients will be instructed to immerse the appliance in 150 ml cup with tap water and dissolve one cleansing (**Albanna *et al.*, 2017**) tablet for 20 minutes according to the manufacture instructions.

Group 3: Combination of the chemical and mechanical methods first submitted to the mechanical method, followed by the chemical method (**Oliveira *et al.*, 2009**).

At the end of the study period, the acrylic samples will be removed carefully and applied into a petri dish containing PBS via a sterile tweezer. The samples will be then immersed twice in a 25ml sterile tubes containing

PBS to remove the planktonic bacteria and inserted into 5ml bijou tube containing 1mm PBS and 5 sterile glass beads. The sample will be vortex-mixed for 1 min to disseminate the biofilm and create a homogenous solution. Ten-fold serial dilutions will be carried out in PBS before the samples are plated onto blood agar (BA), to give the total anaerobic count, mitis salivarius agar (MS), a selective agar for streptococci and Mannitol salt agar (MA) for Staphylococci spp. BA and MS plates will be incubated anaerobically for 2-4 days at 37°C using anaerobic cabinet whereas the MA will be incubated for 2 days in aerobic condition. All organisms from both selective and nonselective agars will be distinguished by colony morphology and will be characterized by Gram reaction (**Al Groosh *et al.*, 2011**) and other confirmatory tests.

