Confirmatory test

1. Catalase testing: Catalase is a common enzyme found in nearly all living organisms exposed to oxygen (such as bacteria, plants, and animals) (**Chelikani *et al.*, 2004**). This test demonstrates the presence of catalase, an enzyme that catalysis the release of oxygen from hydrogen peroxide (H₂O₂). The catalase test is mainly used to differentiate between Gram-positive cocci: members of the genus Staphylococcus are catalase-positive, and members of the genera Streptococcus and Enterococcus are catalase-negative (**Whittenbury, 1964**).
2. Coagulase testing: Coagulase is a protein enzyme produced by several microorganisms that enables the conversion of fibrinogen to fibrin. In the research laboratory, it is used to differentiate between different types of Staphylococcus isolates. Importantly, *S. aureus* is generally coagulase-positive (**Ryan and Ray, 2004**).

Statistical analysis

All the data of the tested samples will be collected and analyzed using SPSS (statistical package of social sciences). In this study the following statistics will be used:

Descriptive statistics

- Mean.
- Standard deviation (SD).
- Minimum and maximum values.
- Statistical tables, figures and charts.

Normality test

Data distribution will be tested first using Shapiro-Wilk test to find that whether our collecting data are normally distributed or not.

Inferential statistics

- ANOVA (if the data parametric) or Kruskal Wallis test (if none parametric) to compare the effect of each cleaning agents on biofilm reduction of removable orthodontic appliance and Tukey HSD pot hoc test if there is significant difference between them.
- Independent t-test (if the data parametric) or Mann Whitney test (if none parametric) to compare the effect of each cleaning agents on biofilm reduction on polished and unpolished surface

In the statistical evaluation, the following levels of significance will be used:

Non-significant NS $P > 0.05$

Significant S $0.05 \geq P > 0.01$

Highly significant HS $P \leq 0.01$

Time table:

Duty	Expected time
Patient Identification and allocation	4 months
Intervention period	3 months
Data collection and analysis	2 months
Writing up the thesis	10 months (starting from the beginning of the study)
Total expected time to finish	About 10 to 11 months

Budget and Funding: The study is self-funded

Dissemination: Master Thesis.

References

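### Aim 2 asks one question about polishing, but the plan names no single deciding surface test; read as one unadjusted test per regimen, the nominal false-claim rate is 14.3% per count

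*Combined protocol and SAP*

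**What the plan says.** The second aim (Aims of the study) is a single question: "To find out if surface modification i.e. polished acrylic fitting surface, have an impact on cleaning the biofilm formation".

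The matching analysis is the second bullet under Inferential statistics. It prescribes "Independent t-test (if the data parametric) or Mann Whitney test (if none parametric") and gives its purpose as "to compare the effect of each cleaning agents on biofilm reduction on polished and unpolished surface". The significance labels that follow call any P of 0.05 or less significant, and 0.01 or less highly significant.

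The only multiplicity procedure is in the first bullet, the comparison of regimens by ANOVA or Kruskal-Wallis: "Tukey HSD pot hoc test if there is significant difference between them".

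On design, Method for biofilm detection states "The volunteer will be grouped into three groups", and Sample size states "Thirteen orthodontic patients for each group will be selected to wear a removable orthodontic appliance for the study period". That makes 3 x 13 = 39 patients. Each appliance has four tile positions, and the tiles are seated at random. The text implies, but does not state outright, that each mouth carries both polished and unpolished tiles; the figure that would settle this is not shown.

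**The concern.** A two-sample test cannot compare three regimens at once, so with the word 'each' the bullet reads most naturally as polished versus unpolished within each regimen. That is three tests per culture count, in three separate sets of patients, for one question. The plan names no overall surface contrast, no order of testing, no adjustment and no exploratory label.

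Two things follow. Under the plan's own labels, one significant regimen out of three could be reported as showing that polishing matters. And if the three tests disagree, nothing says which of them answers Aim 2. The second gap depends on no assumed correlation or variance.

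This is separate from the multiplicity created by three culture counts. It arises within a single count and would remain if one count were made primary.

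**Working it through.** **Inputs.** From the documents: 3 regimens in separate patients, 13 patients per regimen, 0.05 per test, an independent two-sample test, no adjustment. Assumed: two-sided tests, normal data (for instance log counts), complete data, both surfaces in each mouth. The within-mouth correlation is not given, so a range is shown. The plan states no error rate for the surface tests, so there is no figure of its own to reproduce.

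**Step 1: nominal rate.** The regimens use different patients, so the three tests are independent:

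1 - (1 - 0.05)^3 = 1 - 0.857375 = 14.3% per count.

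This needs each test to have a true size of 5%. In simulation (40,000 runs, 13 per group) paired t-tests gave about 14.1% to 14.6% at every correlation from 0 to 0.7.

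**Step 2: the unpaired t-test as written, one value per surface per patient.** With within-mouth correlation r, the true variance of the mean difference is (1 - r) times what the independent t-test assumes. The test is therefore conservative when r is positive. The family rate is 1 - (1 - simulated size)^3:

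| r | Size of one test | Rate over three regimens |
|---|---|---|
| 0 | 4.9% | 14.1% |
| 0.1 | 4.0% | 11.4% |
| 0.2 | 3.2% | 9.2% |
| 0.3 | 2.2% | 6.4% |
| 0.5 | 0.9% | 2.7% |
| 0.7 | 0.1% | 0.4% |

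Separate runs gave about 4% at r = 0.4 and 2.5% at r = 0.5; runs differ by a few tenths of a point. The rate passes below 5% at r between 0.35 and 0.4. Mann-Whitney behaves alike: 13.2%, 5.5% and 2.6% at r = 0, 0.3 and 0.5.

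**Step 3: replicate tiles treated as independent.** Four positions could mean two tiles per surface, and nothing says that tiles are averaged. Analysed as 26 versus 26 values per regimen, the rate over three regimens is 14.1% with no correlation. It is 6.9% with a patient variance share of 0.3 and no patient-by-surface component. With a patient-by-surface share of 0.3, it is 16.0%, 21.1% and 24.3% at patient shares of 0.3, 0.1 and 0. The rate can therefore lie on either side of 14%.

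**Step 4: after the fix.** One deciding contrast at 0.05 has a 5% error rate per count. If the smallest of the three within-regimen P values must meet 0.05/3 = 0.0167, the chance of any false claim when no regimen has an effect is 1 - (1 - 0.0167)^3 = 4.9%.

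**Step 5: power (noncentral t, paired differences).**

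- Effect common to all regimens, standardised difference 0.5: 86% for the overall test on 39 patients (36 degrees of freedom), against 38% for one regimen of 13 at 0.05.
- Effect of 0.9 in one regimen only: that regimen's test has 85% at 0.05 and 68% under Holm. The overall test sees an average effect of 0.9/3 = 0.3 and has about 45%.

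**The case against.** The strongest objection is to a reading that is easy to slip into: that this plan has a 14% false-claim rate, well above 0.05. The documents do not support that. They specify an unpaired test and give no correlation. If the surfaces share a mouth and each patient contributes one value per surface, the rate may be anywhere from about 14% to under 1%, and is below 5% once the correlation reaches about 0.4. This objection stands, so 14.3% must be called nominal. It does not remove the point. A conservative, mis-specified test is no planned control of error, and the full 14.3% appears once the pairing is respected.

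Second, three tests per count is a reading. The regimen bullet uses the same words about each cleaning agent for one omnibus test, so 'each' does not prove separate tests. The surface bullet could mean a single pooled test, with no family within a count. This stands too. The per-regimen reading is the more natural, but the text does not settle it, and the same clarification is needed either way.

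Third, Aim 2 concerns impact on cleaning, so regimen-specific effects may be of interest in themselves. That is a fair reason not to make within-regimen claims depend on a significant overall test. With an effect of 0.9 in one regimen only, such a gate would cut power for that regimen from 68% under Holm to about 38%.

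**Conclusion.** The concern holds in a limited form. Aim 2 has no deciding surface contrast and no rule for discordant results, and Tukey HSD does not cover the surface tests. On the per-regimen reading, the nominal chance of at least one false surface claim is 14.3% per count with correctly sized tests. Under the unpaired t-test as written, with both surfaces in one mouth and one value per surface per patient, it is about 14%, 6%, 4% and 2.5% at correlations of 0, 0.3, 0.4 and 0.5. It may be lower or higher than 14% if replicate tiles are treated as independent.

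A reader might infer that inflation above 5% is certain; it is not, because neither the correlation nor the handling of tiles is given. The figures rest on two-sided tests, normal complete data and the inferred placement of both surfaces in each mouth. This is a cheap improvement to the plan rather than a demonstrated failure of error control.

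**What to change.** Under Inferential statistics, name one deciding test for Aim 2: the within-patient polished-minus-unpolished difference, with tiles averaged per surface per patient, over all 39 patients and allowing for regimen, at 0.05. Report the three within-regimen paired comparisons as secondary with Holm-adjusted P values, without requiring the overall test to be significant first, or label them exploratory. Confirm in the text that every appliance carries both surfaces.

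The change is to wording only and needs no new data. The cost falls on regimen-specific effects: where polishing acts in one regimen only, that regimen's test loses power under Holm (85% to 68% at 0.9) and the overall test is weak (about 45%). The gain comes where the effect is common to all regimens (86% against 38% at 0.5).
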